Appendix 7 - Quantitative Textural Analysis

A Quantitative Radiomics Approach

[figure not shown]
Recent data acquisition and analytical advances have expanded the traditional role of medical imaging beyond subjective/qualitative arenas. Radiomics refers to the comprehensive analyses of tumor phenotypes based on quantifiable image features (1). Quantitative CT-based tumor and tissue texture analysis (QTA) provides comprehensive, 3-dimensional and temporal analyses of tumor heterogeneity (1). This approach represents an emerging technology that can conceivably monitor tumor development, progression, immune cell activity and response to treatment. Tumor heterogeneity on cross-sectional imaging is manifested by histopathological differences in cell density, necrosis, and hemorrhage (2,3). Image texture analyses assess tumor heterogeneity in accordance to the distribution and relationship of pixel or voxel-gray levels in the image (4). Findings from several studies have suggested that imaging texture reflects tumor-host interactive status within the tumor microenvironment (5,6). CT tumor texture analysis has shown promise in predicting pathologic features, overall survival, and response to therapy in NSCLC (1,7-9), colorectal cancers (3,5), esophageal cancer (10), head and neck cancers (11) and metastatic renal cell cancer (13). For, example, Aerts have examined 440 quantitative features that define tumor image intensity, shape and texture extracted from CT scans of 1,019 patients with NSCLC or head and neck cancers and has shown an association between tumor patterns and outcomes through unsupervised clustering analyses of Radiomic expression patterns and demonstrated associations with primary tumor stage (T stage), overall stage, and histology in 422 Stage I/II NSCLC patients (1). Using a prognostic signature that comprised the top features of tumor image intensity, shape, texture, and multiscale wavelet findings, QTA were better than tumor volume and TNM staging in survival prediction by Kaplan Meier analyses. Features describing heterogeneity in the primary tumor were associated with worse survival, whereas patients with more compact/spherical tumors had better survival probability. In separate studies, we have shown prognostic QTA signature that differentiated K-ras mutant NSCLC tumors from pan-wild type NSCLCs (9). We have recently demonstrated that using QTA, a specific imaging QTA signature of kurtosis and entropy is associated with interchromosomal aberrations in mPDA as determined by NGS and that these imaging features are associated with PFS and OS (12). Furthermore, preliminary work from our core lab by QTA analysis from the standard of care baseline CT scans from 28 subjects with metastatic solid tumors treated with PD-1 therapy demonstrated a distinct texture signature that distinguished which tumors were going to respond to PD-1 therapy. Finally, an analysis of the texture of tissue and tumors from subjects treated with paracalcitol showed a distinct texture pattern in the liver and pancreas of mPDA subjects on both the pre treatment and early post treatment scans leading to texture differences that may be distinctive based on vitamin D levels measured in patient serum. These encouraging results provide the rationale for using QTA to explore differences in tumor and tissue texture between the two arms of this study using baseline to and post treatment scans. Such information would be informative and provide a basis for establishing a complementary diagnostic biomarker that could 1) predict disease stability in the maintenance environment 2) provide an imaging signature that is associated with immune infiltrative activity, 3) allow a non invasive method for detecting tumor and tissue texture changes related to vitamin D exposure and 4) identify other correlations of imaging to tumor biology, response, laboratory assessments.

In order to perform Quantitative Textural Analysis (QTA) the following steps are required- De-identified dicomm encoded CT scans will be sent to [REDACTED] for analysis. Images will be reviewed to ensure appropriate series, images and anatomic coverage is available and that all PHI has been removed. Only query free studies will be forwarded for analysis. Query-free scans will be loaded onto [REDACTED] QTA analysis platform for textural analysis. Standard reconstructed algorithm generated image series will be evaluated for presence or absence of evaluable tumor, i.e. tumor ≥ 10 mm containing clearly defined tumor margins on at least two consecutive slices. Polygon ROI tools will be selected and an ROI will be posited around the mid-slice section of the tumor lesion or tissue of interest such as the liver, pancreas, lung, and muscle.

QTA will be applied to regions of interest which uses an image filtration-histogram technique whereby the filtration technique applies a Laplacian of Gaussian band-pass filter enhanced algorithm leading to extracted features of different sizes based on the spatial scale filter (SSF) value varying from fine-texture (SSF2, 2 mm in radius), medium texture (SSF3, 3 mm in radius), and coarse-texture (SSF4, 4 mm in radius). This is followed by quantification of tumor texture from the filtered histogram based texture maps producing the following quantitative parameters

- a) Mean (a measure of average brightness within the ROI)
- b) Kurtosis (K, a measure of peakedness and tailedness)
- c) Skewness (S, a measure of asymmetry of the histogram)
- d) Standard-deviation (SD, a measure of variation or dispersion that exists from the mean)
- e) Mean Positive Pixel (MPP, a measure of pixels that contain non-fat/air densities)
- f) Entropy (a measure of orderliness based upon co-occurrence matrix principles)

A Sample Output from QTA Analysis of Lung Metastasis Lesions is shown below

The resulting Signature Readout file will be forwarded to IE’s data management site and entered into a secure database for marker analysis. Additional IE published Radiomics features may be extracted on the imaging slice (e.g. DVP signs, feature convergence, AB index, etc) as appropriate for tumor size, location and pattern features. Clinical team will supply IE with appropriate data to perform bioinformatics linkage with clinical and genomic data for surrogate marker testing. IE Data Management Team will perform full QC on entered data and manage query resolution process. The expected statistical analysis of the data will involve a non-parametric Mann Whitney test used to assess the ability of the QTA, clinical, and patient characteristics to differentiate between early disease relapses, immunoinfiltration, vitamin D levels, molecular characterization and relapse risk. We anticipate using a recursive-type decision tree (or similar) approach to determine whether the differentiation between these outcomes could be improved by sequential application of QTA parameters. The QTA parameter that most accurately identifies the selected dependent variable will be used in the entire patient cohort as the first node, thereby generating two branches. The abilities of additional QTA parameters to identify outcomes will then be separately tested for each branch, adding further nodes to the tree. The diagnostic threshold values for the QTA parameters used at each node will be optimized using Receiver Operator Characteristic (ROC) analysis to maximize diagnostic accuracy. QTA parameters will be applied in order of overall accuracy for determination between early disease relapses, immunoinfiltration, molecular characterization and relapse risk. If two modalities have the same accuracy, the modality with the highest sensitivity will be applied first. No further node will be added to a branch if the misclassification rate in that branch is less than 15%. The final decision tree will be applied to the whole cohort to determine the

overall sensitivity, specificity, and accuracy. Since this is an exploratory study, General mixed linear modeling and/or computer simulation analysis will be sought to link early disease relapses, immunoinfiltration, vitamin D levels, molecular characterization and relapse risk with QTA results. In our prior work a Monte Carlo analysis using 1,000 iterations of the decision tree was used to assess the impact of uncertainty in the sensitivity and specificity for each QTA parameter (expressed as their 95% confidence intervals [CI]) on the overall diagnostic performance of the decision tree. For early disease relapses and relapse risk, univariate Kaplan-Meier survival (KM) analysis will assess the relationship between the above. An iterative procedure will also be applied to identify the optimal cut off for each marker that provides the best separation of the population into 'good' and 'poor' prognosis groups (indicated by the best p-value from log-rank test). Due to small numbers, we might need to censor reporting results for significant features yielding less than 10 patients per group for comparison to avoid overstating significant results. Additionally, we will focus on analysis for SSF0 through 4, because we believe that there will be a small numbers of cases having QTA measures for SSF 5 mm in radius and above in cases of tumors that are approximately 1 cm. Multivariate Cox regression will be used to determine which significant univariate parameters along with their interactions are independent predictors of recurrence, metastasis and relapse, along with the hazard ratio (HR) and the CI. A two-tailed P value of less than 0.05 will be considered to indicate a significant difference.

Cited References

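### Appendix 7's exploratory texture decision tree is tuned and scored on the same patients (at most 24) with no validation, and its log-rank cut-offs are chosen by best p-value with no correction

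*Protocol*

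**What the plan says.** Protocol section 8.3.6.4 hands the quantitative textural analysis (QTA) to Appendix 7. The SAP is limited by its title to clinical endpoints and does not mention QTA, so Appendix 7 is the operative plan.

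The tree is tentative: "We anticipate using a recursive-type decision tree (or similar) approach". Its construction is then described in some detail:

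- The most accurate parameter "will be used in the entire patient cohort as the first node, thereby generating two branches".
- Thresholds at each node "will be optimized using Receiver Operator Characteristic (ROC) analysis to maximize diagnostic accuracy".
- Further parameters are tested within each branch, and "No further node will be added to a branch if the misclassification rate in that branch is less than 15" per cent.
- "The final decision tree will be applied to the whole cohort to determine the" overall sensitivity, specificity and accuracy.

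The following text says that "General mixed linear modeling and/or computer simulation analysis will be sought to link early disease relapses" and other outcomes with the QTA results. It also mentions a Monte Carlo analysis from the group's previous studies, which addressed uncertainty in each parameter's sensitivity and specificity.

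For prognosis, an iterative search will "identify the optimal cut off for each marker that provides the best separation of the population", judged by the best log-rank p-value. On small numbers, the authors say that "we might need to censor reporting results for significant features yielding less than 10 patients per group". The one significance level given is two-sided 0.05, in a sentence that follows the Cox regression text.

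**The concern.** The patients used to choose the parameters and thresholds are the patients used to score the tree. Appendix 7 names no hold-out set, cross-validation, optimism correction, permutation test, pruning or depth limit. The mixed-modelling and simulation sentence names no validation method, and the Monte Carlo step concerns a different uncertainty. With up to 30 candidate features and at most 24 patients, such a tree can fit chance patterns closely.

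The survival cut-offs raise a related problem. The smallest of many log-rank p-values is not itself a valid p-value, and no adjustment for the search is stated.

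What is at stake is the credibility of any texture signature taken from this trial into later work. The trial's efficacy and safety conclusions are not at stake.

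**Working it through.** **Inputs.** The plan gives no accuracy, error rate or sample size for QTA, so there is no QTA figure to reproduce. The number of patients comes from the main design (Protocol 4.1 and 8.2): 12 per arm, 90% power, one-sided 0.05. Exact enumeration of the one-sided Pearson test reproduces this: 90.1% for 1/12 against 7/12, and 90.3% for 0.08 against 0.58. So n is at most 24.

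Appendix 7 lists 6 texture parameters and focuses on filter scales SSF0 to SSF4: 6 × 5 = 30 features per region of interest, with 6 as a low case. Early relapse is not defined, so event counts of 8, 12 and 16 are assumptions. The design rates imply 24 − (1 + 7) = 16 patients progressing by 6 months.

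**Step 1: what the stopping rule implies.** Suppose every terminal branch b, with n_b patients and e_b errors, meets e_b < 0.15 × n_b. Summing over branches, total errors < 0.15 × 24 = 3.6, so at most 3. Accuracy is then at least 21/24 = 87.5%. The features do not enter this calculation.

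**Step 2: simulated trees.** The first node is always placed. Later nodes are added while branch error is 15% or more. Splits maximise ROC accuracy, with ties broken by sensitivity. The range of results over settings and implementations is:

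| Features | Apparent accuracy | Honest accuracy |
|---|---|---|
| Pure noise | about 91–95% | 50–58% on new patients |
| One real marker, AUC 0.85 | 92–95% | 66–70% on new patients (12 events, 18 or 30 features) |
| One real marker, AUC 0.99 | about 97–99% | not computed |

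Always guessing the larger class gives 67%, 50% and 67% for 8, 12 and 16 events. The AUC 0.85 marker's apparent accuracy exceeded that of a noise data set 44–54% of the time, about a coin toss. Scored by 4-fold cross-validation it did so 73–87% of the time.

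**Step 3: if the 10-per-group limit also governed the tree.** A first split with at least 10 on each side leaves at most 24 − 10 = 14 in a branch. A second split would need 20, so only one split is possible. Noise then shows about 70–77% (50–60% by 8-fold cross-validation) and the AUC 0.85 marker 80–83%.

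**Step 4: best-p log-rank cut-offs.** For one noise marker with n = 24 and 40,000 runs, the chance that the best p-value falls below 0.05 is:

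| Minimum per group | No censoring | 25% censored |
|---|---|---|
| 10 (the plan's tentative limit) | 13.8% | 13.7% |
| 5 (illustrative) | 31.6% | 30.9% |
| 2 (illustrative) | 48.7% | 47.1% |

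Across 30 markers with the limit enforced, 30 × 0.138 = 4.1 false positives are expected, against 30 × 0.05 = 1.5. A fixed median split gives 6.1%. A permutation-adjusted maximally selected test gives 4.6–5.5%.

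**The case against.** The strongest reply is that the text does not order splitting to go on until 15% is reached. It says when a branch receives no more nodes and is silent on what happens when no further parameter helps. That is correct: the result above 85% is conditional on splitting until the rule is met. It still matters, because no other stopping rule is given.

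Four stronger readings are tempting, and the documents do not support them.

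- *No real marker could be told from noise.* This holds for a moderate marker. It fails for a near-perfect one, and it fails under the 10-per-group limit, where noise and the AUC 0.85 marker separate.
- *Apparent accuracy on noise can never fall below 87.5%.* That needs every branch to reach the rule. If each parameter may be used only once on a path, with 6 features, the lowest value seen was 79%. With a very unbalanced outcome (20 against 4) the mean was 89–92%, where the larger class alone gives 83%.
- *The trial's biomarker aim rests on the tree's accuracy.* In Appendix 7 the sentence about a basis for a complementary biomarker follows the comparison of texture between arms, which this problem does not touch. Tree accuracy is not a listed endpoint.
- *The false-positive rate of the cut-offs is 30–50%.* Those rates use minimum group sizes that the plan does not state.

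It is also fair to say that the plan is labelled exploratory, is hedged throughout, and shows awareness of small numbers. This lowers the severity. It does not supply a validation step or a correction: the group-size limit is optional and does not account for the search.

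**Conclusion.** The point holds at low severity. Appendix 7 states a rule that gives optimistic accuracy figures, and nothing elsewhere in the protocol or SAP corrects it. If branches are split to the stated rule, noise would be reported at about 91–95% accuracy when its accuracy on new patients is 50–58%, and an AUC 0.85 marker would look about the same. The best-p cut-offs give about 14% false positives per noise marker with at least 10 per group enforced, and more if that limit is not applied.

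The sizes rest on assumptions that the documents do not fix: a binary outcome, 8 to 16 events of 24, 6 to 30 features, and no depth limit. Applying the 0.05 level to the cut-offs is an inference from its place after the Cox text. The primary and secondary endpoints, the Mann-Whitney tests and the listed comparison of texture between arms are unaffected.

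**What to change.** Amend Appendix 7 as follows.

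- **Label and benchmark.** Call whole-cohort figures apparent accuracy and print the majority-class rate beside them.
- **Validate.** Report performance from repeated stratified cross-validation, or a .632+ bootstrap, with all parameter selection and threshold tuning repeated inside each resample. Add a permutation p-value. Simple bootstrap optimism subtraction is not enough: on noise it still left 75–78%, against 51–60% for .632+. Leave-one-out runs low for a balanced outcome at this size (45–47% on noise with 12 events).
- **Cut-offs.** Replace the best-p search with the continuous marker in a Cox model, or with a permutation-adjusted maximally selected log-rank test. Make the 10-per-group limit firm. If it also governs the tree, each training set needs at least 20 patients; 8-fold cross-validation leaves 24 − 3 = 21.

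The cost is protocol wording and some computing time, with no new data. Reported accuracy will be lower and imprecise: 18 of 24 correct (75%) has an exact 95% interval of about 53–90%, treated as a simple binomial. Power is modest. An AUC 0.85 marker reached a permutation p of 0.05 or less in about 51% of simulated trials with 6 features and 12 events, and in 27% with 30 features and 8 events.

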Primary: To estimate the percentage of patients progressing at 6 months by RECIST1.1 when maintained on a combination regimen of paricalcitol plus pembrolizumab versus pembrolizumab alone.

Secondary:

1. Evaluate the toxicity of the combination of paricalcitol plus pembrolizumab versus pembrolizumab alone.
2. Evaluate the difference in overall survival (OS) in patients administered the combination of paricalcitol plus pembrolizumab versus pembrolizumab alone.
3. Define the impact of the combination of paricalcitol and pembrolizumab on tumor mutational landscape and transcriptional programs.
4. Identify cellular VDR targets in the immune microenvironment with PD1 blockade.

Exploratory:

1. Evaluate the difference in disease progression according to iRECIST vs. RECIST 1.1 criteria (Appendix 5)
2. Assess the utility of a Patient Personalized Clinical Benefit (PPCB) phone-based

| |
|---|
| 
application
 
 3. Assess the association between improvement in symptoms as recorded by the Patient Personalized Clinical Benefit (PPCB) with progression at 6 months by RECIST 1.1 4. Assess any changes in tumor and/or tissue texture on imaging in both arms of the trial 5. To monitor and compare the gut microbial communities in both arms of the trial. |
| 
Trial Design: Randomized Double Blind, Placebo Controlled
 |
| 
No. Patients: Total of 24, 12 randomized to each treatment arm
 |
| 
Name, dose of drugs:
 
 • Pembrolizumab (Keytruda®) 200 mg administered as an intravenous infusion over 30 minutes every 3 weeks. • Paricalcitol (Zemlar®) 25 mcg administered intravenously 3 times per week (given on days 1, 3, 5, 8, 10, 12, 15, 17, 19 ± 1 day of each 21 day cycle) and prior to each pembrolizumab infusion. • Placebo- equivalent volume administered intravenously, 3 times per week and prior to each pembrolizumab infusion. |
| 
Treatment Arms: Arm1: pembrolizumab + paricalcitol Arm 2: pembrolizumab + placebo (saline solution)
 |
| 
Patient Population: Patients with stage IV pancreatic cancer who have been put in best response, defined as: Must have obtained a best response of at least stable disease (SD) or partial response (PR) for a period of 2 months with no further shrinkage of ≥ 30% on scan.
 |

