8.2 Sample Size Considerations

The primary endpoint is the percentage of patients progressing at 6 months. Based on a contemporary control of no maintenance after best response to prior chemotherapy⁸, the control arm with pembrolizumab alone is expected to have only 8% of patients with no progression at 6 months. To be of clinical interest, at least 58% of patients must be progression-free at 6 months on the pembrolizumab plus paricalcitol arm. A sample size of 12 patients per arm will provide 90% statistical power to detect this difference assuming a one-sided alpha level of 0.05. A one-sided test was selected as we are only interested in the combination if it decreases the percentage of patients progressing at 6 months. This sample size estimate was obtained using binomial enumeration of all possible outcomes to compare two independent binomial proportions (Pearson's chi-squared test) using PASS 15.¹⁸ A statistical concern is that the Pearson chi-squared test does not guarantee the alpha level. We confirmed that we have adequate statistical power using the Miettinen & Nurminen¹⁹ exact likelihood score method (89% power) using Pass 15.

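### Appendix 7 leaves open withholding texture cut-off results because they are significant in small groups, which would make reporting of that exploratory analysis depend on the result

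*Protocol*

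**What the plan says.** Protocol section 8.3.6.4 refers the QTA analysis to Appendix 7. The SAP covers clinical endpoints and does not mention QTA, so Appendix 7 is the only specification.

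For relapse outcomes, Appendix 7 plans Kaplan-Meier analysis by marker and a search for the cut-off: "An iterative procedure will also be applied to identify the optimal cut off for each marker that provides the best separation", with best separation "indicated by the best p-value from log-rank test". The threshold is then given: "A two-tailed P value of less than 0.05 will be considered to indicate a significant difference". No correction for the search is stated, and the search has no minimum group size.

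Directly after the search comes the sentence at issue. Because numbers are small, "we might need to censor reporting results for significant features yielding less than 10 patients per group for comparison to avoid overstating significant results". The wording is tentative. It does not say when the option would be used, whether one group or both must be below 10, or what happens to non-significant features with equally small groups.

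The Trial Synopsis gives the sample size as "Total of 24, 12 randomized to each treatment arm". The number usable for QTA is not stated and may be lower: "Only query free studies will be forwarded for analysis", and tumour features need an evaluable tumour of at least 10 mm.

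**The concern.** A minimum group size is a reasonable safeguard if it is set before the results are seen and applied to every feature. This one depends on the result twice. It is aimed only at features that have reached significance, and the group sizes come from a cut-off chosen to minimise the p-value. It is also discretionary, so withholding could be decided with the results in hand.

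An exploratory marker analysis is useful when readers can see everything that was tested. If significant results are withheld according to where the search happened to cut, the published set is a filtered one, and real markers can be lost with the false ones.

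**Working it through.** **Inputs.** N = 24 (Synopsis); cut-off by smallest log-rank p, two-sided 0.05, fewer than 10 per group (Appendix 7). The documents give no marker effect sizes and no figure for the share of markers withheld, so the effects below are assumptions.

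**The plan's own figure.** N = 24 comes from section 8.2: "A sample size of 12 patients per arm will provide 90% statistical power to detect this difference assuming a one-sided alpha level of 0.05". Exact enumeration with progression-free rates of 1/12 and 7/12 gives 90.1% (stated 90%). The Miettinen-Nurminen score method gives 88.8% (stated 89%). Both reproduce. This confirms N only and says nothing about QTA.

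**Counting splits.** A cut divides N patients into k and N − k, with k = 1, …, N − 1. Both groups reach 10 when 10 ≤ k ≤ N − 10, which is N − 19 splits if N ≥ 20.
- N = 24: 24 − 19 = 5 of 23 survive, so 18 of 23 (78%) leave a group under 10.
- N = 20: 20 − 19 = 1 of 19 survives, the 10/10 split.
- N < 20: none survives.

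This reads the sentence as either group under 10. If both had to be under 10, the total could be at most 9 + 9 = 18, and nothing could be withheld at N = 24.

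**Simulating the search.** Every cut is scanned, the smallest log-rank p is kept, and it is called significant at p < 0.05. Share reported = share significant × (1 − share withheld). Settings: N = 24, no censoring, 6,000 to 10,000 runs per scenario. With 20% censoring the withheld shares agree within about 1.5 points.

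| True marker | Significant | Withheld, of significant | Reported |
|---|---|---|---|
| None | 61% | 91% | about 6% |
| Continuous, HR 1.5 per SD | 86% | 84% | 0.86 × 0.16 = 14% |
| Continuous, HR 2 per SD | 97% | 81% | 0.97 × 0.19 = 18% |
| Continuous, HR 3 per SD | 100% | 79% | 1.00 × 0.21 = 21% |
| Threshold at median, HR 2 | 78% | 76% | 0.78 × 0.24 = 19% |
| Threshold at median, HR 3 | 91% | 64% | 0.91 × 0.36 = 33% |
| Threshold at median, HR 5 | 98% | 51% | 0.98 × 0.49 = 48% |
| Threshold at median, HR 8 | 100% | 46% | 1.00 × 0.54 = 54% |

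For a real effect confined to the top quarter of patients (HR 3 to 5), 89-90% are withheld. If the search already requires at least 5 per group, the withheld shares are 75% (null), 68-71% (continuous), 39-60% (median threshold) and 81-87% (top quarter). Across all these scenarios the range is 39-91%. At N = 20 the null figure rises to 98%.

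**Comparison with a continuous Cox model.** These runs use the planned progression rates, 18 months' follow-up, a normally distributed marker and at least 2 patients per side.
- Null marker: the search is significant in about 48%, falling to about 6% after withholding, so 1 − 6/48 = 87.5% are withheld. Cox gives about 5%.
- Continuous effect, HR 1.65 (2.2) per SD: 81% (79%) of significant results withheld and 15% (20%) reported. Cox detects 36% (68%).
- Threshold at the median: 42-58% withheld, with no power advantage for Cox. A separate run without censoring, HR 3, gave 46% for Cox against 38% reported under the restriction, which is a small gain at most.

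**The case against.** The strongest defence is that the sentence does what it sets out to do. An uncorrected cut-off search on 24 patients calls a null marker significant in about half of trials or more, and the restriction brings that down to about 6%. In most scenarios it also removes null markers more often than real ones. This stands. Deleting the sentence and keeping the search would make reporting worse.

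The sentence is also tentative. A reader might infer a firm rule that suppresses four in five significant markers. The text supports only an option without a criterion, and about 80% belongs to one assumed shape, a continuous effect under a full or nearly full scan. The missing criterion is itself a weakness.

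A reader might further infer that the QTA objective cannot be met, or that nothing significant could be reported below 20 usable patients. The documents do not support this. The stated endpoint in section 3.6 is the texture difference between arms, 12 against 12 at full enrolment, and Appendix 7 plans other analyses too (Mann-Whitney tests, a decision tree, mixed models, Cox regression). The sentence follows the search for good and poor prognosis groups and is best read as attached to it. For the same reason, reading the groups as progressed against not progressed is speculative.

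Nor does Appendix 7 say that non-significant features with small groups would stay in the report, or that the number of features tested would be hidden. It is silent on both.

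**Conclusion.** The point holds, at minor severity. If the option is used, with either group under 10 as the trigger, reporting of the QTA cut-off analysis depends on the result, and a substantial share of real markers would be withheld along with false ones. At 24 patients this is about 80% of significant results for a continuous effect, about 40-75% for a threshold near the median, and about 87-91% for a null marker under a full or nearly full scan. The 39-91% range covers the scenarios tried; it is not a bound. The split count (18 of 23) needs no model; the other shares rest on assumed effect sizes, effect shapes and search limits.

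The advantage of a continuous Cox model also depends on shape. It is clear for a continuous effect and small or absent for a threshold at the median. The firmer argument for the change is complete reporting at about 5% false positives per feature. The between-arm texture comparison and the primary and secondary analyses are not affected.

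**What to change.** In Appendix 7, remove the best-p-value cut-off search and the withholding sentence together, not the sentence alone. In their place, state that:
- every QTA feature tested is reported, whatever its p-value, with the number of evaluable patients;
- each has a hazard ratio per SD with 95% CI from a Cox model using the feature as a continuous covariate, so no minimum group size is needed;
- any Kaplan-Meier plot uses a median split fixed in advance for all features.

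The cost is appendix wording and a longer results table. Tuned good and poor prognosis cut-offs are given up, and no power gain should be expected if the true effect is a threshold at the median. No new data, patients or procedures are needed.
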